Targeting Worry to Improve Sleep

NCT03684057

June 5, 2019

Procedures:

Individuals will be recruited primarily via online advertising (e.g. Facebook and Google AdWords). Those who learn about the study via social media will be prompted to complete an online screening questionnaire. Those who learn about the study via other means (e.g. flyers, word of mouth) will review the questions from the online screener during the initial screening phone call. After the screening call, eligible participants will be scheduled for their baseline visit at the Brown Mindfulness Center ([name]). Study staff will send potential participants a copy of the consent form to review prior to the baseline visit. Participants will be asked to complete four study visits in total: three visits will be in-person and one will be completed online.

At the baseline visit, potential participants will be asked to review the consent form, ask any questions they may have about the study and if they decide to participate in the study, they will be asked to sign the consent form. Study participants will be given a copy of the signed consent form for their records.

Randomization Plan: A research team member who is not involved with the study will prepare sealed envelopes with an individual's group assignment using a block randomization scheme designed by an independent statistician. After the consent process and prior to administration of assessments, study participants will be randomized into one of two groups: 1) Group A – the treatment as usual group; 2) Group B - the UA intervention group. The participant will be given a sealed envelope and asked to open it to determine their group assignment.

Based on the participant's group assignment, the research team member will pull up the appropriate survey in Qualtrics and ask the participant to complete the first portion of the baseline assessment. After they have concluded, they will be instructed on how to complete the shape-matching task and then left alone to complete it on the study laptop while the researcher keeps track of the time from outside.

Upon completion of the assessments, the participant will be instructed to download either the Fitbit app (Group A) or Unwinding Anxiety and the Fitbit app (Group B). Please see below for onboarding specific to group assignment.

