If the participant is randomized to Group A - They will be given a Fitbit Inspire to track the quality of their sleep and asked to download the Fitbit app to their smartphone. They will be provided with the information necessary to set up their account and instructed how to use the app to track their sleep. Please refer to the included script, *Fitbit Setup Guide* attachment, for more details. They will be asked to wear the Fitbit and record what time they went to bed & woke up in a sleep diary (which will be provided) for one week after the baseline visit, one week before the 3rd visit (in-person), and one week before the 4th visit (in-person). The total number of hours slept per night will be collected for the post-baseline period in Qualtrics via a personalized survey link while data will be collected in person for the other two use periods and recorded in Qualtrics. Upon completion of the third assessment, the UA app will be downloaded to his/her smartphone at no cost and with lifetime access. The participant will be instructed to watch the first module of the app and will review its features with the research team member to ensure they do not have any questions (see *UA Setup Guide* attachment for more details).

If the participant is randomized to Group B - They will be given a Fitbit and the process outlined above will be followed. In addition, the UA app will be downloaded to his/her smartphone and the same process will be followed as outlined above.

Both groups are expected to complete the following tasks / assessments at each research visit:

Baseline – In-person

- Group A will complete the first eight items using a personalized survey link (based on participant ID) via Qualtrics

- Group B will complete the first seven items using a personalized survey link via Qualtrics and the seventh, the GAD-7, will be completed as part of the Unwinding Anxiety assessment.
- Both groups will complete the shape matching task on a study laptop.
 1. Demographics. This form will be filled out in Qualtrics (age, gender, socioeconomic status, employment, education, race/ethnicity, relationship status) (approximately 3 minutes)

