 2. Five Facet Mindfulness Questionnaire (FFMQ) non-reactivity scale. The non-reactivity scale is a subscale of the 39-item FFMQ which is a self-report psychological measure of mindfulness skills. This subscale contains 7 items which are presented on a 6-point Likert scale ranging from 1 (almost always) to 6 (almost never). This questionnaire is included in the protocol. (approximately 1 minute)
 3. Penn State Worry Questionnaire (PSWQ). The PSWQ is a 16-item self-report measure of worry with items presented on a 5-point Likert scale ranging from 1 (not at all typical of me) to 5 (very typical of me). This questionnaire is included in the protocol. (approximately 3 minutes)
 4. Multidimensional Assessment of Interoceptive Awareness (MAIA). The MAIA is a 32-item self-report questionnaire comprised of 8 subscales including: noticing, not-distracting, not-worrying, attention regulation, emotional awareness, self-regulation, body listening, and trusting. Items are rated on a 6-point Likert scale ranging from 0 (never) to 5 (always). This questionnaire is included in the protocol. (approximately 5 minutes)
 5. PROMIS Sleep & Anxiety items. The PROMIS Sleep & Anxiety includes 5 questions taken from the PROMIS v1.0 Sleep Disturbance questionnaire which focus on the interaction between worry and sleep. This questionnaire is included in the protocol. (approximately 1 minute)
 6. Worry Interfering with Sleep scale (WIS). The WIS is a single item self-report question that asks individuals to rate what percent of time worry interfered with their ability to get to or stay asleep. This questionnaire is included in the protocol. (approximately 1 minute).
 7. Expectancy. These three questions assess treatment usefulness, confidence, and likelihood to recommend on a 9-point Likert scale from 1 (Not at all confident or Not at all useful) to 9 (Very confident or Very useful) and from 0 to 100%. This questionnaire is included in the protocol (approximately 1 minute).
 8. Generalized Anxiety Disorder 7-items (GAD-7). The GAD-7 is a 7-item measure of anxiety rated on a 4-point Likert scale ranging from 0 (Not at all sure) to 3 (Nearly every day). This questionnaire is included in the protocol. (approximately 2 minutes)

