3. $\geq 5/10$ on Worry Interfering with Sleep scale (WIS)
4. Able to read and speak English, because the Unwinding Anxiety app is available in English only.
5. Owns a smartphone (UA app can only be used on a smartphone)
6. Willingness to wear the Fitbit Inspire tracker

Exclusion:

1. If using psychotropic medication - not on a stable dosage for at least 6 weeks
2. Medical disorder of the severity that would interfere with ability to participate (e.g. cancer, multiple sclerosis, Parkinson's disease, ALS, etc. These disorders impact sleep quality which could confound study outcomes.)
3. As needed (i.e. prn) benzodiazepine or hypnotic sleep aid
4. Known sleep disorder (e.g. obstructive sleep apnea, restless leg syndrome – because these disorders impact sleep quality.)
5. Psychotic disorder (Mindfulness meditation has to be carefully monitored with people experiencing psychosis. We are not able to provide this type of monitoring given budget constraints.)
6. Post-Traumatic Stress Disorder (Mindfulness meditation has to be carefully monitored with people experiencing PTSD. We are not able to provide this type of monitoring given budget constraints.)
7. Severe Depression (PHQ-2 score > 3) (People experiencing severe depression may also experience sleep disorders which could confound study outcomes.)
8. Current shift work employment (People working alternate shifts may have sleep quality problems which could confound study outcomes.)
9. BMI > 30. (People who are obese may have sleep quality problems which could confound study outcomes.)
10. Evening caffeine use (Caffeine use late in the day can impact the quality of a person's sleep, hence the possibility of confounding study outcomes.)
11. Pregnancy (Women in various stages of pregnancy often have sleep quality problems, hence the possibility of confounding study outcomes.)
12. New parents whose child is not sleeping through the night (New parents are often awakened every 3 – 4 hours by a newborn which could confound study outcomes)
13. Lives in same household as someone already enrolled in this study (To prevent study participants from sharing study information with one another.)

Participant enrollment target:

Our goal is to collect 64 complete and usable data sets, so our plan is recruit and enroll 80 participants.

Enrolling 80 participants will be sufficient to cover any participants who don't complete the study and it will allow us to meet our N of 64.

Check-ins

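### For TST, SE and SPT the SAP's baseline wear week falls after randomization, with the app installed in Group B only, so the change-score GEE estimates the 2-month effect minus any week-1 effect

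*Combined protocol and SAP*

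**What the plan says.** The order of events at the baseline visit is set out under Procedures and Randomization Plan. Allocation comes first: "After the consent process and prior to administration of assessments, study participants will be randomized into one of two groups". The participant opens the envelope, so the arm is known. The questionnaires and the shape-matching task follow. Then: "Upon completion of the assessments, the participant will be instructed to download either the Fitbit app (Group A) or Unwinding Anxiety and the Fitbit app".

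Under the Group A onboarding text, the Fitbit and diary are used "for one week after the baseline visit, one week before the 3rd visit (in-person"), with a third week before the fourth visit. The same paragraph calls the first of these the post-baseline period. Group B follows the same Fitbit process, and "In addition, the UA app will be downloaded to his/her smartphone and the same process will be followed as outlined above". Group A has no app until later: "Upon completion of the third assessment, the UA app will be downloaded to his/her smartphone".

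The Statistical Analysis Plan names 2 months as the primary endpoint, with Welch or Mann-Whitney tests there. It adds a GEE that regresses change in each outcome on time, group and their interaction. Its sleep paragraph applies the same approach to the sleep measures and adds a complete-case analysis that leaves out people who did not complete the baseline wear period. It also models missingness on baseline values of the outcome.

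**The concern.** A change score has its usual meaning only if the starting value precedes treatment. Three wear weeks are scheduled and the first is the only one that can serve as a baseline, but Group B already has the app during it and Group A does not. Any early effect of the app on sleep is then subtracted from the later effect, and a reader who sees change from baseline will take it as change from a pre-treatment value that was never collected.

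The complete-case rule raises a second, smaller issue. Whether someone completes that week is behaviour after open allocation, so the rule selects participants on something the arm could influence.

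**Working it through.** **Reproducing a stated figure.** The plan gives no effect size, SD, correlation, alpha or power for sleep, so there is nothing to reproduce. The only design figure is the target: "Our goal is to collect 64 complete and usable data sets, so our plan is recruit and enroll 80 participants". Everything numerical below is an illustration.

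**What the change-score GEE estimates.** Let the group difference (B minus A) be δ1 in week 1 and δ2 at 2 months. Randomization makes the arms equal in expectation before the app, so the expected group difference in change at 2 months is δ2 − δ1. Writing δ1 = f·δ2, this is δ2(1 − f). A simulation with 400,000 participants and δ2 = 0.70 SD agreed: f = 0, 25% and 50% gave 0.70, 0.53 and 0.35 SD.

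**Illustrative inputs (assumed).** 32 per arm (64 complete sets, 1:1), two-sided alpha 0.05, δ2 = 0.71 SD. A comparison of 2-month values has SE = √(2/32) = 0.25 SD and power 80%.

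**A reasoned value for f.** If the effect builds linearly over two calendar months, compare the midpoints of the two wear weeks. Two months is 2 × 365.25/12 = 60.9 days, so the midpoints are day 3.5 and day 60.9 − 3.5 = 57.4, and f = 3.5/57.4 = 6.1%. This is an assumption: Group B's third visit is tied to Module 30, not to a date, so f cannot be derived from the documents.

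**Change-score estimate, 0.71 × (1 − f).**

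| f | Estimate (SD) | Shift (SD) | Power at r = 0.5 |
|---|---|---|---|
| 0 | 0.71 | 0 | 80% |
| 6.1% | 0.67 | −0.04 | 75% |
| 25% | 0.53 | −0.18 | 55% |
| 50% | 0.36 | −0.36 | 29% |
| −6.1% (opposite sign) | 0.75 | +0.04 | 84% |

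**Precision at f = 6.1%.** The SE of a change score is 0.25 × √(2(1 − r)), where r is the correlation between the two weeks. RMSE is √(SE² + 0.043²).

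| r | SE | RMSE | Power |
|---|---|---|---|
| 0.3 | 0.296 | 0.299 | 60% |
| 0.5 | 0.250 | 0.254 | 75% |
| 0.7 | 0.194 | 0.198 | 92% |

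For 2-month values the RMSE is 0.250. Adjusting for baseline-visit scores with an assumed correlation of 0.3 gives 0.25 × √(1 − 0.09) = 0.238 and 83% power. The change score therefore has the smaller RMSE once r exceeds 0.56 at f = 6.1%. At r = 0.7 it keeps that advantage until f reaches about 20%.

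**Complete-case selection.** In a simulation with no treatment effect, r = 0.5 and an assumed 80% or so completing week 1, completion depended on stable sleep level in Group B only. At log-odds slopes of 0.25, 0.5 and 1.0 per SD, the difference in 2-month values was biased by 0.04, 0.07 and 0.14 SD. The difference in change scores stayed within 0.01 SD of zero. Selection tied to a stable level is present in both weeks and cancels on subtraction.

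**The case against.** The strongest case on the other side has four parts.

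*The effect is small and unknown.* On the one reasoned assumption the shift is 0.04 SD against an SE of 0.25 SD, and the sleep measures are not named as primary. This stands, and it limits the weight of the point.

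*The plan already holds much of the remedy.* The complete-case analysis is an addition, and the next sentence turns to the ITT analysis, with weighting and pattern-mixture models. The exclusion therefore most naturally belongs to the complete-case analysis alone. The 2-month tests most plainly mean 2-month values, which are unaffected. Both readings are reasonable, but neither is stated, and neither changes what the GEE estimates.

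*The change score may be more precise.* This stands when sleep is highly correlated over time. A further alternative, 2-month values with week-1 sleep as a covariate, has RMSE 0.239, 0.218 and 0.181 at r = 0.3, 0.5 and 0.7 (f = 6.1%), as good as or better than the 0.238 above. It conditions on a post-randomization measurement, so its bias also grows with f. The choice is a trade-off, but an estimate of δ2 − δ1 should not be reported as the 2-month effect.

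*Several stronger inferences fail.* A reader might infer that week-1 completion will differ by arm because those hours come "via a personalized survey link while data will be collected in person for the other two use periods". The survey link is the same in both arms and cannot by itself cause a difference. The 7-day check-in, which at that point reaches Group B only, concerns the app rather than Fitbit wear. A reader might take 64 of 80 as the week-1 completion rate, but it refers to complete data sets overall. The 3-day rule for TST might be read as voiding 2-month data when week 1 is missing, but it reads naturally as a threshold applied period by period. Finally, the complete-case biases above concern 2-month values and should not be carried over to the GEE.

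**Conclusion.** The point holds for TST, SE and SPT. The sequence of randomization, app download and first wear week is explicit, and the Procedures and the SAP label that week differently. As written, the adjusted sleep analysis targets the 2-month effect minus any week-1 effect. That conclusion needs no numerical assumption; its size does. With 0.71 SD and 32 per arm assumed, the shift runs from 0.04 SD at a 6% share to 0.36 SD at 50%, and it reverses sign if the week-1 effect is opposite.

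Complete-case selection is a real but conditional risk. It can bias 2-month values if wear relates to sleep differently by arm, and it largely cancels in change scores when wear follows only a stable sleep level.

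A reader might infer that every sleep result, or the primary comparison, is compromised. The documents do not support that. The questionnaire measures ("The PROMIS Sleep & Anxiety includes 5 questions taken from the PROMIS v1.0 Sleep Disturbance questionnaire", and the WIS) are completed before the app download, although after the envelope is opened. The 2-month Welch or Mann-Whitney test is sound if run on values. Nor is it a fault to use observed week-1 sleep to model missingness; the only difficulty is that the value may itself be missing. This is worth correcting, mainly so that the estimate is properly described and the right analysis leads.

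**What to change.** Amend the SAP wording:

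1. Call week 1 the first post-randomization wear period, and reconcile the label with the Procedures.
2. State that the 2-month Welch or Mann-Whitney sleep comparison uses 2-month values by randomized arm.
3. In the sleep GEE, model the wear-period values (week 1, 2 months, 4 months) as repeated outcomes on time, group and their interaction. Read the group difference at 2 months, adjusted for baseline-visit PROMIS sleep and WIS scores, described as collected before the app download but after allocation was known.
4. Do not exclude anyone from the ITT sleep analysis for a missing week 1.
5. Report change from week 1 and the complete-case results as labelled sensitivity analyses, with week-1 completion shown by arm.
6. Keep observed week-1 sleep in the missingness weights, and fall back to baseline-visit covariates where it is missing.

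No new data or visits are needed. The cost is some precision if sleep is highly correlated over time: at r = 0.7 and a 6% share, RMSE is 0.238 for adjusted values against 0.198 for change, and power is 83% against 92%. Item 5 keeps the change-score result available.

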 9. Shape Matching Task. The shape matching task assesses cognitive control, or resistance to distraction. Individuals are presented with probe and target shapes and must decide whether they are the same shape. On some trials a distractor shape will be present, which the individual is instructed to ignore. (approximately 25 minutes)

Module 14 (Group B) or 1 Month (Group A) – Online

- Both groups will receive a personalized survey link via Qualtrics.

1. FFMQ non-reactivity (approximately 1 minute)
2. PSWQ (approximately 3 minutes)
3. MAIA (approximately 5 minutes)
4. PROMIS Sleep & Anxiety (approximately 1 minute)
5. WIS (approximately 1 minute)
6. GAD-7 (approximately 2 minutes)

Module 30 (Group B) or 2 Months (Group A)

- Group A will complete the first five items using a personalized survey link via Qualtrics and the sixth, the GAD-7, will be completed as part of the Unwinding Anxiety assessment.
- Group B will complete the first seven items using a personalized survey link via Qualtrics
- Both groups will complete the shape matching task on a study laptop.
 1. FFMQ non-reactivity (approximately 1 minute)
 2. PSWQ (approximately 3 minutes)
 3. MAIA (approximately 5 minutes)
 4. PROMIS Sleep & Anxiety (approximately 1 minute)
 5. WIS (approximately 1 minute)
 6. GAD-7 (approximately 2 minutes)
 7. Net promoter score (approximately 1 minute)
 8. Shape matching task (approximately 25 minutes)

2 Months post-intervention (Group B) or 4 Months (Group A)

- Both groups will complete the first six items using a personalized survey link via Qualtrics and the shape matching task will be completed on a study laptop.
 1. FFMQ non-reactivity (approximately 1 minute)
 2. PSWQ (approximately 3 minutes)
 3. MAIA (approximately 5 minutes)
 4. PROMIS Sleep & Anxiety (approximately 1 minute)

5. WIS (approximately 1 minute)
6. GAD-7 (approximately 2 minutes)
7. Shape matching task (approximately 25 minutes)

4. Participant Population.

Description of participant population:

We will recruit people who experience sleep disturbances related to anxiety in order to address Aims 1 & 2 of this study. We will recruit people who live within a 30-minute drive of Providence, RI because people who live within close proximity to Providence are more likely to return for follow-up visits and complete the study.

Participants will meet the following criteria:

Inclusion:

1. 18 years or older
2. PSWQ > 40 based on established cut-off suggesting GAD

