Analyses will be conducted in R using an intent-to-treat approach (ITT). Fischer's exact tests for categorical and Kruskal Wallis tests for continuous variables will be used to determine any between-group differences in baseline demographics. To examine between-group differences in behavioral outcome measures at the primary endpoint (2 months), Welch's t-tests will be used along with Mann Whitney U tests for data that violates the assumption of normality. A series of Generalized Estimating Equations (GEE) will be used to estimate the adjusted intervention effect by regressing change in outcomes at each follow-up on time, group, time*group and confounders identified a priori (using correlation analysis. GEE's are used for longitudinal data in order to account for within-subject covariance over time. False Discovery Rate will be used to correct for multiple comparisons.

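### The third visit falls at Module 30 in Group B but at 2 months in Group A, while the SAP tests a single 2-month endpoint, and no visible text reconciles the two

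*Combined protocol and SAP*

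**What the plan says.** The assessment schedule under Procedures names each post-baseline visit differently by arm:

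- second (online): "Module 14 (Group B) or 1 Month (Group A"
- third (in person): "Module 30 (Group B) or 2 Months (Group A"
- fourth (in person): "2 Months post-intervention (Group B) or 4 Months (Group A"

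The Statistical Analysis Plan opens with "Analyses will be conducted in R using an intent-to-treat approach (ITT" and then examines "between-group differences in behavioral outcome measures at the primary endpoint (2 months", with no distinction by arm. The longitudinal model is a GEE "regressing change in outcomes at each follow-up on time, group, time*group and confounders"; whether time means calendar time, module or visit number is not stated.

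Other parts of the plan depend on the visit dates. The later Fitbit and diary weeks fall "one week before the 3rd visit (in-person), and one week before the 4th visit (in-person". Group A receives the app after its third visit: "Upon completion of the third assessment, the UA app will be downloaded to his/her smartphone at no cost".

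The visible text gives no module pace, visit window or latest date, and no rule for a Group B participant who has not reached Module 30. The Check-ins section dates its contacts at days 7, 14 and 45 after app access and gives their purpose as engagement and questions. The reminder calls mentioned under Ongoing Consent have no dates.

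**The concern.** An intention-to-treat comparison at one time needs an outcome that is due at that time in everyone randomized, whatever they did afterwards. Group A's schedule meets this. Group B's, read literally, does not, because reaching a module is behaviour after randomization that only Group B can show. Three consequences follow on that reading.

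- **Timing.** Slow and fast users have a stated visit point, but it falls at a different time since randomization from that of controls.
- **Availability.** A participant who never reaches Module 30 has no stated point for the primary visit and no clear anchor for a visit defined as 2 months post-intervention.
- **Knock-on effects.** The Module 14 survey and the pre-visit wear weeks inherit the same dependence, so the sleep outcomes are affected as well as the questionnaires.

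The direction cannot be predicted. People who stop using the app may be those who are not improving, or those who improved early and saw no need to go on.

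**Working it through.** The plan gives no figure for visit timing to reproduce. Its only relevant count is 80 enrolled to obtain 64 complete data sets (Participant enrollment target), an implied loss of (80 − 64)/80 = 20%.

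**Step 1: the pace at which the schedules agree.** With a month of 30.44 days:

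- Module 14 at 1 month: 14/30.44 = 0.46 modules a day.
- Module 30 at 2 months: 30/60.88 = 0.49 modules a day.

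The two agree closely, which fits the reading that the modules are nominal labels. The schedules coincide only near this pace, about one module every two days.

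**Step 2: timing if the pace differs (paces assumed).** Day of Module 30 = 30/(0.4928 × k), where k is Group B's mean pace relative to nominal.

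| k | Day of Module 30 | Shift from day 60.9 |
|---|---|---|
| 0.75 | 81.2 | +20.3 days |
| 1 | 60.9 | 0 |
| 1.25 | 48.7 | −12.2 days |

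At the extremes, one module a day gives day 30, about 31 days early. One module every four days gives day 120, about 59 days late and close to Group A's fourth visit.

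**Step 3: what a shift could do (drift assumed).** Suppose both arms drift by 0.1 to 0.3 SD a month and the app has no effect. The spurious difference is drift × shift/30.44:

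- late: 0.1 × 20.3/30.44 = 0.07 SD, up to 0.3 × 20.3/30.44 = 0.20 SD;
- early: 0.04 to 0.12 SD in the opposite direction.

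If half of Group B were slow and half fast at these paces, the mean shift would be (20.3 − 12.2)/2, about 4 days, and the difference 0.013 to 0.040 SD.

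**Step 4: what selective absence could do (all inputs assumed).** Take 40 per arm, no true effect and the 20% loss spread evenly, so that 32 are compared with 32. Standard error = sqrt(2/32) = 0.25 SD. Let the least engaged 20% be lost, with correlation ρ between engagement and improvement. Truncated-normal selection gives bias = (ρ_B − ρ_A) × 0.350, where 0.350 = φ(z at 20%)/0.80.

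| ρ_B | Bias, ρ_A = 0 | Type I error | Bias, ρ_A = ρ_B/2 | Type I error |
|---|---|---|---|---|
| 0.1 | 0.035 SD | 5.2% | 0.018 SD | 5.1% |
| 0.3 | 0.105 SD | 7.0% | 0.053 SD | 5.5% |
| 0.5 | 0.175 SD | 10.8% | 0.088 SD | 6.4% |

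For ρ_A = 0, simulating 40,000 trials with Welch's test gave 5.2%, 6.8% and 10.9%. Equal selection in both arms gives no bias, and a negative correlation reverses the sign. These figures are for an unadjusted test on those observed, not for the planned missing-data analyses.

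**Step 5: whether the planned methods repair it.** The weighting model in the Statistical Analysis Plan predicts missingness from baseline covariates and the baseline outcome. Engagement after baseline is not in it, so missingness driven by engagement is captured only as far as baseline data predict it. Pattern mixture models are planned for the case where missing at random fails, so they do address absent outcomes. Neither method corrects outcomes that were observed at different times in the two arms.

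**The case against.** The strongest reply is that Module 30 is only shorthand for month 2. The SAP names one 2-month endpoint without distinguishing arms. The fourth-visit heading, by pairing 2 months post-intervention with 4 months, places the end of the intervention at month 2. The two implied paces nearly match. Procedures expects both groups to complete every visit, and the compensation section names no module condition. On this reading non-finishers are seen at 2 months and most of the bias argument falls away. Attachments that are cited but not shown, such as the app setup guide or the main consent form, may also state a pace or a fallback.

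Much of this stands. A reader might infer that completing Module 30 is the operative trigger; the documents do not support that as fact, because the schedule consists of headings and no sentence makes a visit conditional on a module. But no visible sentence says that Group B is seen by calendar either, and using post-intervention for Group B alone points the other way. Staff could not tell from this text whether to book a Group B participant at 2 months who is short of Module 30, or to wait.

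A reader might also infer that weighting and pattern mixture models are planned only for sleep data, because they appear in that paragraph. The text does not support this: sleep analysis follows the behavioral approach, and the two methods are introduced for the intention-to-treat analysis generally.

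Assessment at the end of a programme is a recognised design, and a wear week could be arranged as a participant nears Module 30. Neither point covers a participant who does not get there.

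**Conclusion.** The schedule and the endpoint are stated in different terms and need reconciling. This is more than missing detail, because following the headings literally would make the timing and availability of the primary outcome depend on adherence in one arm. It should be fixed, with moderate confidence, since the label reading is plausible and some supporting material is not visible.

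A reader might take the illustration as evidence that the primary comparison is biased. It is not. Pace, drift, equal allocation, even loss and every correlation are assumed, and the results run from no bias to 0.175 SD for selective absence and up to 0.20 SD for timing, in either direction. The conclusion rests on the conflict between the two sections and the absence of a rule for non-finishers, not on those figures.

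**What to change.** Reconcile the assessment schedule with the Statistical Analysis Plan:

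- Assess both arms at 1 and 2 months from randomization within one common stated window, whatever module Group B has reached.
- Give the last visit a calendar anchor that also covers non-finishers, for example 2 months after the scheduled 2-month visit.
- Set the pre-visit wear weeks from these dates.
- Define time in the GEE by the scheduled visits.
- Record the module reached at each visit as an adherence variable for the per-protocol analysis.
- Report actual days from randomization to each visit, by arm.

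The cost is protocol wording and the timing of survey links, wear weeks and bookings; no visits are added. There are two downsides. Some Group B participants will be assessed before finishing the app, so the estimate is the effect of offering it. The last visit will no longer fall exactly 2 months after each person's own completion. Nor does the change make the last visit a comparison of app with no app, because Group A has the app by then.
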